8 STUDY DESIGN

8.1 Overview of Study Design

This is a Phase 3, multicenter, open-label, rollover study in subjects with CF who are homozygous or heterozygous for the *F508del-CFTR* mutation and who participated in Studies VX13-661-103, VX14-661-106, VX14-661-107, VX14-661-108, VX14-661-109, VX14-661-111, or other Vertex studies investigating VX-661 in combination with ivacaftor. The study is designed to evaluate the safety and efficacy of long-term treatment of VX-661 in combination with ivacaftor.

A schematic of the study design is shown in [Figure 8-1](#).

This study consists of a Treatment Cohort (eligible subjects 12 years of age and older) and an Observational Cohort (eligible subjects <18 years of age [age on the date of informed consent/assent in the parent study]), which will enroll subjects from Studies VX13-661-103,

VX14-661-106, VX14-661-107, VX14-661-108, VX14-661-109, VX14-661-111, and other Vertex studies investigating VX-661 in combination with ivacaftor. The Treatment Cohort and the Observational Cohort will be open to enrollment in parallel.

Treatment Cohort

Subjects who completed study drug treatment (i.e., VX-661/ivacaftor, ivacaftor monotherapy, or placebo) during the Treatment Period in the parent study who meet the eligibility criteria (Sections 9.1 and 9.2) will be offered the opportunity to enroll in Study VX14-661-110. Subjects who permanently discontinue study drug treatment or who withdrew consent during the parent study are not eligible for enrollment in the Treatment Cohort.

Subjects in the Treatment Cohort will receive VX-661 100 mg/ivacaftor 150-mg fixed-dose combination (FDC) tablet daily (qd) in the morning and ivacaftor 150-mg tablet qd in the evening. The Treatment Period will be approximately 96 weeks.

Subjects may screen for another qualified Vertex study while participating in the Treatment Cohort.

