12.3.2 Overview of Analysis Strategies

- Study VX14-661-110 data will not be analyzed in isolation as patients received different durations of treatment in the parent studies. Study VX14-661-110 data will be integrated with the parent study data for each subject from the first active dose of VX-661/ivacaftor or ivacaftor alone (after the washout period, if applicable).
- The analysis baseline will be the last non-missing measurement prior to the first active dose of VX-661/ivacaftor or ivacaftor alone [in the parent study (after the washout period, if

applicable) or Study VX14-661-110]. All post-baseline measurements will be mapped to the uniform analysis visit windows based on the study days counted from the first active dose of VX-661/ivacaftor or ivacaftor alone (after the washout period in the parent study, if applicable) to make the results more comparable and interpretable.

- For subjects in Study VX14-661-110, the safety analyses will be performed on all of the subjects pooled together. The efficacy analysis will be performed on each CFTR mutation group separately (*F508del/F508del*, *F508del/Residual Function*, and *F508del/Gating*).

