7.1 Efficacy Analysis Sets

The **Full Analysis Set (FAS)** is defined as all enrolled subjects who have received at least 1 dose of study drug in Part A and have one of the following mutations: *F508del/F508del (F/F)* and *F508del/Residual function (F/RF)*. The FAS is to be used in the efficacy analyses unless otherwise specified.

Study 106 and 108 were the basis for the approval of TEZ/IVA. Although Study 107 and 109 subjects were rolled over to FAS in Study 110, after the study results were available, subjects from Study 107 and 109 were early discontinued from Study 110. Thus, the efficacy analysis will focus on the **106/110 Efficacy Set (ES)** and **108/110 ES**, defined as all the FAS subjects rolling over from Study 106 and 108 respectively.

As shown in [Table 7-1](#), treatment group assignment is based on the randomized treatment in parent study. For 108/110 ES, the randomized treatment assignment in Period 2 will be used to assign subjects to a treatment group in Study 110.

Treatment Group	Description
TEZ/IVA	Subjects randomized to TEZ/IVA in parent study
PBO-TEZ/IVA	Subjects randomized to placebo in parent study
IVA-TEZ/IVA	Subjects randomized to IVA in parent study

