7.2 Pulmonary Exacerbation Analysis Sets

106/110 PEx Analysis Set and **108/110 PEx Analysis Set** are defined in **Error! Reference source not found.**. They include the subjects who received TEZ/IVA in parent study or Part A.

Analysis Population Name	Treatment Group	Description
106/110 PE Analysis Set	TEZ/IVA	Subjects randomized to TEZ/IVA in Study 106 and received treatment
	PBO-TEZ/IVA	Subjects randomized to placebo in Study 106 and who received TEZ/IVA in Study 110
108/110 PE Analysis Set	TEZ/IVA	Subjects randomized to IVA-TEZ/IVA sequence or PBO-TEZ/IVA sequence in Study 108 and who received treatment in Period 2 of Study 108
	IVA-TEZ/IVA	Subjects randomized to TEZ/IVA-IVA sequence or PBO-IVA sequence in Study 108 and who received treatment in Period 2 of Study 108 and who received TEZ/IVA in Study 110. Subjects in TEZ/IVA-IVA sequence who did not enroll in Study 110 treatment cohort will also be included in this group if they received treatment in Period 1.
	PBO-TEZ/IVA	Subjects randomized to TEZ/IVA-PBO sequence or IVA-PBO sequence in Study 108 and who received treatment in Period 2 of Study 108 and who received TEZ/IVA in Study 110. Subjects in TEZ/IVA-PBO sequence who did not enroll in Study 110 treatment cohort will also be included in this group if they received treatment in Period 1.

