8 ANALYSIS PERIODS

8.1 Efficacy Analysis Period

110 Efficacy Analysis Period is defined as the time period from the 1st dose of study drug in Part A to the date of last efficacy assessment in Part A.

For subjects who participate in another qualified Vertex study before completing Study 110 assessments and re-enroll in Study 110, 110 Efficacy Analysis Period will exclude the time between the last dose before the discontinuation from Study 110 and the first dose after re-enrollment in Study 110.

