9.6.2 Analysis of Efficacy Endpoints

Most continuous endpoints during 110 Efficacy Analysis Period will be analyzed for subjects in 106/110 ES and 108/110 ES using a mixed-effects model for repeated measures (MMRM) with similar specification as in the parent study SAP/CSR, if applicable. However, these MMRM analysis will be restricted to the last visit at which the total number of subjects is approximately 70% of subjects from the respective parent study.

These continuous endpoints during 110 Efficacy Analysis Period will also be descriptively summarized for subjects in FAS who roll over from Study 103 and 111, where the patients carry *F/F* mutation.

No hypothesis testing will be done for between-group comparisons.

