9.6.2.4.1 Subjects in 106/110 ES and 108/110 ES

The similar analysis will be performed as the analysis of absolute change in ppFEV₁ from baseline for 106/110 ES or 108/110 ES during 110 Efficacy Analysis Period. However, in the MMRM models of all other efficacy endpoints, the terms involving parent study baseline ppFEV₁ will be replaced by similar terms involving the corresponding endpoint in parent study. Similarly, the results based on MMRM along with descriptive statistics for observed values and absolute changes from baseline will be presented at scheduled visits within each treatment group, and LS means ($\pm 95\%$ CI) for absolute change from baseline at each visit will also be plotted by treatment groups.

9.6.2.4.2 Subjects in FAS Who Roll Over from Study 103 and 111

For subjects in FAS who rolled over from Study 103 and 111 respectively, descriptive summary statistics of observed values and absolute or relative changes from baseline in these efficacy endpoints will be provided at scheduled visit during 110 Efficacy Analysis Period.

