	Week 24	Study 110 Week 24	169	[142, 211]
	Week 36	Study 110 Week 36	253	[212, 295]
	Week 48	Study 110 Week 48	337	[296, 379]
	Week 60	Study 110 Week 60	421	[380, 463]
	Week 72	Study 110 Week 72	505	[464, 547]
	Week 84	Study 110 Week 84	589	[548, 631]
	Week 96	Study 110 Week 96	673	[632, 687]
	ETT	ETT	N/A	Follow the individual visit window to be mapped to individual visits
	Safety Follow-up Visit	Safety Follow-up Visit	N/A	Follow the individual visit window to be mapped to individual visits if fall within the upper boundary of the window for the last scheduled visit (Day 687); or remain as SFU if otherwise.

Note:

1. To apply the above visit windows, please first label Day 1 for the date of the first dose in Study 110 drug, and use the nominal visit names to label SFU (for safety).
2. After the SFU (for safety) measurements are determined; the above visit windows will be applied to determine the analysis visit names for all remaining measures at scheduled or unscheduled visits.
3. For all efficacy parameters, if there are multiple measurements within a visit window, the record at the scheduled visit will be used. Otherwise,
 - If there are no measurements at the scheduled visit, then the record closest to the target day will be used;
 - If there are multiple records with the same distance to the target day, the latest record will be used.
 - Assessments at the early treatment termination (ETT) visit will follow the windowing rules for regular visits.
 - Assessments at safety follow-up (SFU) visit will follow the windowing rules for regular visits if they fall within the upper boundary of the window for the last scheduled visit; it will remain as the SFU if it goes beyond the upper boundary of the window for the last scheduled visit.
4. For all safety parameters, if there are multiple measurements within a visit window, then 1) the record closest to the target day will be used, with the exception of the threshold analysis in which the worst record will be used; 2) if there are multiple records within the same distance of the target day, the latest record will be used; or 3) the SFU visit will not be windowed; instead, the nominal visit will be used in relevant analysis.

Special handling for ECG:

- On Day 1 & Day 15, ECGs will be collected before dosing and at 1.5 and 4 hours after the morning dose. None of the measures on Day 1 or Day 15 will be mapped into other visits.

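### Continuous efficacy is analysed on Study 110 visits only, although the protocol integrates parent-study data; separately, both documents restrict it to rollover subjects

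*SAP*

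**What the plan says.** (TEZ is the SAP's name for VX-661.)

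**Period and time axis.** Protocol 12.3.2 says: "Study VX14-661-110 data will not be analyzed in isolation as patients received different durations of treatment in the parent studies". It then integrates each subject's parent data from the first active dose of VX-661/ivacaftor or ivacaftor alone, and counts analysis visits from that dose. Protocol 12.3.1 defines the Efficacy Analysis Period in the same way and, for Study 108, places the first active dose in Treatment Period 2.

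The SAP takes another course. Section 8.1 says that the "110 Efficacy Analysis Period is defined as the time period from the 1st dose of study drug in Part A". Section 9.6.2 applies it: "Most continuous endpoints during 110 Efficacy Analysis Period will be analyzed for subjects in 106/110 ES and 108/110 ES". Section 9.6.2.4.1 carries CFQ-R, BMI, weight and the z-scores along, "for 106/110 ES or 108/110 ES during 110 Efficacy Analysis Period". Section 11.1 tells the programmer to "first label Day 1 for the date of the first dose in Study 110 drug". Under SAP 9.1 the efficacy baseline is the parent-study baseline for everyone except subjects randomised to placebo in Study 106, who take a Study 110 baseline.

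**Who is included.** SAP 7.1 describes the 106/110 and 108/110 Efficacy Sets as "defined as all the FAS subjects rolling over from Study 106 and 108 respectively". The protocol's Full Analysis Set (12.2) likewise requires a Study 110 dose. On Treatment Cohort entry, Protocol 8.1 says: "Subjects who permanently discontinue study drug treatment or who withdrew consent during the parent study are not eligible".

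**Exacerbations are handled differently.** For the TEZ/IVA group of the 106/110 exacerbation set, SAP 7.2 takes "Subjects randomized to TEZ/IVA in Study 106 and received treatment", with no rollover requirement. SAP 8.2 counts from the first TEZ/IVA dose.

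**The concern.** There are two issues, with different origins.

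(a) The SAP departs, without explanation, from the protocol's stated strategy on which visits enter the model and where time zero lies. The protocol's reason for integrating was that parent treatment durations differ. Starting every arm at Study 110 Day 1 brings that problem back.

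(b) Under either document, subjects who stopped TEZ/IVA in the parent study contribute nothing to the continuous efficacy estimates. They have no rows in the MMRM, so its missing-at-random assumption cannot recover them.

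Long-term efficacy is the secondary objective. At stake are what the change-from-baseline curves describe, and whether the ppFEV1 and exacerbation results under the TEZ/IVA label can be read together. The SAP does not say that they cover different subjects and periods.

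**Working it through.** **1. Stated totals.** Enrolled (SAP 6.2): 23 + 464 + 159 + 227 + 138 + 33 = 1,044, as stated. Potentially eligible (Protocol synopsis): 40 + 490 + 300 + 300 + 200 + 45 = 1,375, as stated. No power calculation is given, and SAP 9.6.2 plans no between-group tests.

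**2. The two clocks, arm by arm.**

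| Arm | Protocol clock starts | SAP clock starts | SAP baseline | Parent visits on active drug dropped |
|---|---|---|---|---|
| 106 TEZ/IVA | first Study 106 dose | first Study 110 dose | parent | yes |
| 106 PBO-TEZ/IVA | first Study 110 dose | first Study 110 dose | Study 110 | none to drop |
| 108 TEZ/IVA | first Period 2 dose | first Study 110 dose | parent | yes (Period 2) |
| 108 IVA-TEZ/IVA | first Period 2 ivacaftor dose | first Study 110 dose | parent | yes (Period 2) |
| 108 PBO-TEZ/IVA | first Study 110 dose (Period 2 rule) | first Study 110 dose | parent | none to drop |

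So the departure affects three of the five arms. Subjects from Studies 103 and 111 receive descriptive summaries over the same Study 110 period.

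**3. Time since baseline in 106/110.** Let P be the parent-study duration in weeks. At Study 110 Week X, the time since baseline is P + X for TEZ/IVA and X for PBO-TEZ/IVA. SAP 9.6.2.1.1 fits both arms with one visit factor and plots LS means by visit.

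The documents do not give P for Study 106. Protocol 8.2.2 puts total treatment at up to approximately 2.5 years:

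- 2.5 × 52.18 = 130.45 weeks
- 130.45 − 96 = 34.45 weeks
- 34.45 / 130.45 = 26.4%

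This is a ceiling across all parent studies, not the Study 106 value. At that ceiling, Week 8 would mean about 42 weeks since baseline in one arm and 8 in the other.

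**4. Who is in the sets.** The protocol's FAS and the SAP's efficacy sets both need a Study 110 dose, and permanent parent-study discontinuers cannot have one. Adding parent visits for FAS subjects, as the protocol plans, restores their early on-treatment visits and a common axis. It does not bring back the discontinuers. That needs a different set, such as the 106/110 exacerbation set.

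**5. Scale of the selection (illustration only).** Let p be the share not rolling over and d the amount by which their mean ppFEV1 change is worse. The rollover-only mean then exceeds the all-subject mean by p × d. The only available p compares enrolled with planned eligible counts, all arms pooled:

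- Study 106: (490 − 464)/490 = 26/490 = 5.3%
- Study 108: (300 − 227)/300 = 73/300 = 24.3%, where 300 is an 'up to' figure

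| Assumed d (points) | 106: p × d | 108: p × d |
|---|---|---|
| 1 | 0.05 | 0.24 |
| 2 | 0.11 | 0.49 |
| 5 | 0.27 | 1.22 |

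No value of d appears in the documents, and p is not the share of treated TEZ/IVA subjects who discontinued.

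**The case against.** The best defence is that an extension study describes those who extend. The set definition says so openly, visits are labelled as Study 110 weeks, baselines are defined, arms are estimated separately and nothing is tested between them. Exacerbations are a rate with an exposure offset, whereas ppFEV1 is a change at a visit, so different periods can be legitimate. The SAP is also written for a protocol with Parts A and B, which the public protocol does not describe; an amendment may explain the change, and that cannot be checked here.

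Much of this stands. It limits how serious the point is and shows that rollover conditioning is not a slip. It does not supply the missing reason for leaving the protocol's integration, and a Study 110 week label does not tell the reader that time since baseline differs by arm. SAP 7.1 explains the focus on Studies 106 and 108, but not the loss of parent visits.

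A reader might go further in three ways that the documents do not support:

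- **That the SAP's departure causes the selection.** It does not. Eligibility and the FAS cause it, and the protocol shares both.
- **That estimates are conditional on having tolerated the drug.** Protocol 9.1 admits subjects with interruptions who completed their visits, so the condition is completion. It concerns TEZ/IVA only in the TEZ/IVA arms. For 106 PBO-TEZ/IVA the clock is the same in both documents, and the exacerbation set also requires Study 110 treatment.
- **That the exacerbation sets can be reused unchanged.** For Study 108, SAP 7.2 adds some non-rollover subjects treated with TEZ/IVA in Period 1, while SAP 8.2 pools only Period 2.

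**Conclusion.** Both points hold, separately.

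(a) SAP 8.1, 9.6.2 and 11.1 depart from Protocol 12.3.1 and 12.3.2 without a stated reason. They drop parent on-treatment visits for subjects already on active drug and mix times since baseline on the 106/110 visit axis. This needs no assumption about dropout. The omitted TEZ/IVA follow-up is at most about 34 weeks, or 26%.

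(b) In both documents the TEZ/IVA-arm LS means are conditional on completing parent-study treatment, unlike the SAP's 106/110 exacerbation set.

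A reader might infer that the results are shown to favour the drug by the amounts in the illustration. They are not. The counts are planned and cover all arms, eligible subjects may simply have chosen not to enrol, and the deficit is assumed. The direction is plausible; the size cannot be computed without arm-specific treated and discontinued numbers. Since the objective is secondary and no test depends on it, this should be corrected but does not undermine the study.

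**What to change.** In SAP 8.1, 9.6.2 and 11.1:

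1. Add the protocol's integrated MMRM for 106/110 ES and 108/110 ES: parent on-treatment visits (Period 2 for Study 108) plus Study 110 visits, with time counted from the first active dose. Report it beside the Study 110-only model, and state why the latter was chosen.
2. State the baseline for this model. Protocol 12.3.1 gives parent-study ivacaftor subjects a Study 110 baseline, while its general rule and 12.3.2 place baseline before the first active dose, ivacaftor included.
3. As a further supportive run for 106/110, include everyone randomised to and treated with TEZ/IVA in Study 106, as in the 106/110 exacerbation set. For Study 108, limit any such extension to subjects treated with TEZ/IVA in Period 2. This step goes beyond the protocol and should be described as such.
4. Label the rollover-only LS means as being among parent-study completers, and note on the 106/110 plots that time since baseline differs by arm.

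The cost is SAP text, mapping parent visits to a common axis, and extra model runs. The sponsor already pools parent data in part for exacerbations. No new data collection is needed.

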8.2 Pulmonary Exacerbation Analysis Period

PEx Efficacy Analysis Period is defined as the time period from the first dose of TEZ/IVA in parent study (after the washout period, if applicable) or Study 110 Part A to the date of last efficacy assessment in parent study or Study 110 Part A, as highlighted in grey in [Table 8-1](#). Note for parent Study 108, only Period 2 is pooled.

Similarly, for subjects who participate in another qualified Vertex study before completing Study 110 assessments and re-enroll in Study 110, the PEx Efficacy Analysis Period will exclude the time between the last dose before the discontinuation from Study 110 and the first dose after re-enrollment in Study 110.

Table 8-1 PEx Analysis Period for PEx Analysis Sets			
Analysis Set	Analysis Period		
	Parent Study		Study 110 Part A
106/110 PEx Analysis Set	TEZ/IVA		TEZ/IVA
	PBO		TEZ/IVA
108/110 PEx Analysis Set	Period 1: TEZ/IVA	Period 2: IVA	TEZ/IVA
	Period 1: IVA	Period 2: TEZ/IVA	TEZ/IVA
	Period 1: TEZ/IVA	Period 2: PBO	TEZ/IVA
	Period 1: PBO	Period 2: TEZ/IVA	TEZ/IVA

	Period 1: IVA	Period 2: PBO	TEZ/IVA
	Period 1: PBO	Period 2: IVA	TEZ/IVA

8.3 Safety Analysis Period

The safety analysis period is defined as Study 110 Treatment-emergent Period in [Section 9.1](#).

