12.3.5 Safety Analysis (Treatment Cohort)

Evaluating the long-term safety and tolerability of VX-661 in combination with ivacaftor treatment in the Treatment Cohort is the primary objective of this study. All safety analyses will be based on TE Period for subjects in the Safety Set.

The overall safety profile of the combination treatment will be assessed in terms of the following safety and tolerability endpoints:

- Treatment-emergent adverse events (TEAEs), SAEs, TEAEs leading to treatment discontinuations, TEAEs leading to treatment interruptions, deaths.
- Clinical laboratory results (i.e., hematology, serum chemistry, coagulation studies, vitamin levels, lipid panel, and urinalysis)
- Standard 12-lead ECGs
- Vital signs
- Pulse oximetry
- Pregnancy test

Descriptive analysis of safety will be performed for subjects in the Safety Set of Study VX14-661-110.

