- Derivations of measurements at scheduled visits per specified visit windowing rules;
- Derivations of baseline/last on-treatment measurements;
- Derivations of the maximum/minimum on-treatment values and maximum/minimum changes from baseline values for safety analyses;
- Data listings where appropriate.

Treatment-emergent (TE) Period will include the time from the first active dose of VX-661/ivacaftor or ivacaftor alone (in the parent study or Study VX14-661-110, but after the washout period, if applicable) to the Safety Follow-up Visit in Part A or 28 days after the last dose of the study drug for subjects who do not have a Safety Follow-up Visit or who have their Safety Follow-up Visit more than 35 days after the last dose in Part A of Study VX14-661-110. For subjects who participate in another qualified Vertex study before completing Part A of Study VX14-661-110 (96 weeks) and re-enroll in Study VX14-661-110, the TE Period will exclude the time spent in the other study.

110 Treatment-Emergent (TE) Period is defined as the time from 1st dose of study drug in Part A to SFU in Part A or 28 days after the last dose of the study drug for subjects who do not have a SFU Visit or who have their SFU Visit more than 35 days after the last dose in Part A. For subjects who participate in another qualified Vertex study before completing Part A (96 weeks) and re-enroll in Study 110, the TE Period will exclude the time spent in the other study. The **efficacy analysis baseline** is defined as the most recent non-missing measurement (scheduled or unscheduled) collected prior to the first dose of study drug in the parent studies for all subjects, except for subjects randomized to the placebo arm in Study 106.

The efficacy analysis baseline for subjects randomized to the Study 106 placebo arm is defined as the most recent non-missing measurement (scheduled or unscheduled) collected prior to the first dose of study drug in Study 110.

The **safety analysis baseline**, unless otherwise specified, is defined as the last non-missing assessment prior to the first dose of active treatment (TEZ/IVA or IVA) from the parent study (after the wash-out period, where applicable) or Study 110, whichever is earlier.

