11 APPENDICES

11.1 Analysis Visit Window Mapping Rules

Table 11-1 Visit Window Mapping Rules for Safety Measurements

Assessments	Visit	Target Study Day	Visit Window (in study days)

 • Standard 12-lead ECG • Vital signs • Pulse oximetry • Labs 
 ○ Chemistry ○ Hematology 	Day 1	1	[1, 1]
	Day 15	15	[2, 36]
	Week 8	57	[37, 85]
	Week 16	113	[86, 141]
	Week 24	169	[142, 211]
	Week 36	253	[212, 295]
	Week 48	337	[296, 379]
	Week 60	421	[380, 463]
	Week 72	505	[464, 547]
	Week 84	589	[548, 631]
	Week 96	673	[632, 687]
	ETT	N/A	Follow the individual visit window to be mapped to individual visits
Safety Follow-up Visit	N/A	Nominal (remain as SFU)	

 • Coagulation • Lipid Panel • Labs 
 ○ Vitamin Level ○ Urinalysis 	Day 1	1	[1, 1]
	Week 8	57	[2, 85]
	Week 16	113	[86, 141]
	Week 24	169	[142, 211]
	Week 36	253	[212, 295]
	Week 48	337	[296, 379]
	Week 60	421	[380, 463]
	Week 72	505	[464, 547]
	Week 84	589	[548, 631]
	Week 96	673	[632, 687]
	ETT	N/A	Follow the individual visit window to be mapped to individual visits
	Safety Follow-up Visit	N/A	Nominal (remain as SFU)

Note: spirometry assessments, BMI, weight, and height will be used for both efficacy and safety purposes. Their measurements will follow the visit windowing rules for efficacy measurements.

Table 11-2 Visit Window Mapping Rules for Efficacy Measurements

Assessments	Visit	Analysis Visit	Target Study Day	Visit Window (in study days)

 • Spirometry • CFQ-R 	Day 15	Study 110 Day 15	15	[2, 36]
	Week 8	Study 110 Week 8	57	[37, 85]
	Week 16	Study 110 Week 16	113	[86, 141]
	Week 24	Study 110 Week 24	169	[142, 211]
	Week 36	Study 110 Week 36	253	[212, 295]
	Week 48	Study 110 Week 48	337	[296, 379]
	Week 60	Study 110 Week 60	421	[380, 463]
	Week 72	Study 110 Week 72	505	[464, 547]
	Week 84	Study 110 Week 84	589	[548, 631]
	Week 96	Study 110 Week 96	673	[632, 687]
	ETT		N/A	Follow the individual visit window to be mapped to individual visits
Safety Follow-up Visit	Safety Follow-up Visit	N/A	Follow the individual visit window to be mapped to individual visits if fall within the upper boundary of the window for the last scheduled visit (Day 687); or remain as SFU if otherwise.	

 • Weight and height • BMI 	Week 8	Study 110 Week 8	57	[2, 85]
	Week 16	Study 110 Week 16	113	[86, 141]

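### Pooled by-visit safety changes in Study 110 mix subjects with different time on drug, because the baseline precedes the first active dose while visits count from the first Study 110 dose

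*SAP*

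**What the plan says.** Three SAP rules meet in the by-visit safety tables.

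- **Baseline (SAP 9.1).** The safety baseline "is defined as the last non-missing assessment prior to the first dose of active treatment (TEZ/IVA or IVA) from the parent study" (after washout, where applicable) or Study 110, whichever is earlier.
- **Visit clock (SAP 11.1, Note 1).** Programmers are told to "label Day 1 for the date of the first dose in Study 110 drug". The windows in "Table 11-1 Visit Window Mapping Rules for Safety Measurements" then apply to laboratory tests, ECG, vital signs and oximetry.
- **Period and population (SAP 8.3, 7.3).** "The safety analysis period is defined as Study 110 Treatment-emergent Period". The Safety Set is everyone dosed in Part A, and its definition contains no parent-treatment groups.

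On this footing SAP 9.7.2 to 9.7.5 plan raw values and change from baseline by visit. For laboratory tests, SAP 9.7.2 adds shifts by visit and plots of the mean liver-test values.

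SAP 9.1 also keeps a second period, which "will include the time from the first active dose of VX-661/ivacaftor or ivacaftor alone", but SAP 8.3 does not select it for safety.

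The supplied protocol was arranged differently. Section 12.3.2 says that "Study VX14-661-110 data will not be analyzed in isolation as patients received different durations of treatment in the parent studies" and has post-baseline values "mapped to the uniform analysis visit windows based on the study days counted from the first active dose of VX-661/ivacaftor or ivacaftor alone". Section 12.3.5 adds: "All safety analyses will be based on TE Period for subjects in the Safety Set".

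**The concern.** A change from baseline at a named visit is normally read as the change after that much treatment. Here that reading holds only for subjects whose first active dose is the first Study 110 dose. For a subject already on TEZ/IVA or ivacaftor, the change at Study 110 Day 15 spans the parent-study treatment as well.

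One pooled mean therefore averages new starters and continuers at different points of their treatment. If a laboratory or ECG effect appears early and then settles, new starters show it at the early Study 110 visits while continuers may be past it, so the pooled figure is pulled toward the continuers. Long-term safety is the primary objective, and these are its main by-visit displays.

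SAP 9.5 raises a smaller, related question. It defines a cumulative TEZ/IVA exposure from the first TEZ/IVA dose date, yet bases it on the 110 TE Period. The visible SAP does not say which time is the denominator of the exposure-adjusted rates.

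**Working it through.** **1. The plan's own count.** SAP 6.2 lists 23 + 464 + 159 + 227 + 138 + 33 = 1,044, as stated. It does not split these by prior treatment, so the share of continuers cannot be derived. SAP Table 8-1 shows six Study 108 sequences; Period 2 is TEZ/IVA in two, ivacaftor in two and placebo in two. Both placebo-in-Period-2 sequences had TEZ/IVA or ivacaftor in Period 1.

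**2. The two origins side by side.**

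| Treatment immediately before Study 110 | Baseline precedes | Visit days count from |
|---|---|---|
| Placebo | first Study 110 dose | first Study 110 dose |
| TEZ/IVA or ivacaftor | first active parent-study dose (after washout, if any) | first Study 110 dose |

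The origins agree in the first row only.

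**3. Prior time on drug.** Protocol 8.2.2 gives up to approximately 2.5 years in total for subjects on the combination in both studies. Both documents give approximately 96 weeks in Study 110.

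Prior weeks = (years × 365.25 − 96 × 7) / 7

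- 2.5 years: (913.1 − 672) / 7 = 34.4 weeks
- 2.25 years: (821.8 − 672) / 7 = 21.4 weeks
- 2.75 years: (1,004.4 − 672) / 7 = 47.5 weeks (47.49 before rounding)

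The 2.25 to 2.75 range is my assumption for what approximately covers. The documents do not give parent-study durations or the prior time of subjects on ivacaftor alone.

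**4. Weeks on drug at the same Study 110 visit.** A new starter has w weeks; a continuer has up to w + 34.4 (range w + 21.4 to w + 47.5).

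| Visit | New starter | Continuer (range) | Ratio (range) |
|---|---|---|---|
| Day 15 | 2 | 36.4 (23.4–49.5) | 18.2 (11.7–24.7) |
| Week 8 | 8 | 42.4 (29.4–55.5) | 5.3 (3.7–6.9) |
| Week 24 | 24 | 58.4 (45.4–71.5) | 2.4 (1.9–3.0) |
| Week 36 | 36 | 70.4 (57.4–83.5) | 1.96 (1.59–2.32) |
| Week 48 | 48 | 82.4 (69.4–95.5) | 1.72 (1.45–1.99) |
| Week 96 | 96 | 130.4 (117.4–143.5) | 1.36 (1.22–1.49) |

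On a first-active-dose clock, a continuer's Week 24 record (Day 169) with 34 prior weeks is Day 169 + 238 = 407, inside the Week 60 window [380, 463] of Table 11-1.

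**5. Effect on a pooled mean.** Let p be the proportion of new starters at a visit, d(t) the mean change after t weeks on drug, and k the prior weeks. The pooled mean is p·d(w) + (1 − p)·d(w + k). If the effect is present at w and has gone by w + k, this reduces to p·d(w). The dilution is the factor p, which the documents do not give.

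**6. Exposure denominator.** If events in Study 110 alone were divided by time since the first parent-study dose, the rate for a continuer who completes 96 weeks would be too low by 34.4 / 130.4 = 26% (21.4 / 117.4 = 18% to 47.5 / 143.5 = 33%). With time within the 110 TE Period, the understatement is zero.

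**The case against.** The strongest reply is that the effect is limited. The summaries are descriptive. Threshold counts cover the whole 110 TE Period, and adverse event rates within Study 110 are exposure-adjusted, so neither depends on the visit clock. By Week 96 the difference in time on drug is modest, and late visits matter most for long-term safety. Ratios of weeks on drug are also not estimates of bias: 18 at Day 15 says nothing about the size of any laboratory change. All of this stands. What remains is that the early by-visit tables cannot be read as the change after a given time on drug.

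A reader might go further in four ways that the documents do not support.

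- **That the SAP breaches the protocol.** The SAP is written for a Part A and Part B design that the supplied protocol does not contain, so it appears to follow a later version. The protocol text is supporting context; the mismatch lies within the SAP.
- **That adverse events on parent-study drug go unreported.** SAP 9.7.1 plans a treatment-emergent table for each of the six parent studies, and SAP 7.4 presents Study 106 safety alongside. No visible table runs from first active dose through Study 110, but a heading after SAP 9.7.1.4 and a final appendix heading are redacted. An integrated table would also draw its parent-study time only from subjects who completed treatment and rolled over (Protocol 9.1), which can understate rates.
- **That 34 weeks is a hard maximum.** It is a point value from two approximate figures.
- **That the TE period is undefined in SAP 9.7.7 and 11.4.** SAP 8.3 and 9.7.1 settle it as the 110 TE Period.

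**Conclusion.** The point holds for the by-visit outputs. As written, pooled mean changes, laboratory shifts by visit and liver-test plots combine subjects whose time since first active dose differs by 0 to about 34 weeks (about 21 to 47 under the stated range). The mixing is greatest at Day 15 and Week 8 and modest by Week 96. An early effect in new starters can be diluted, by an amount that cannot be computed because neither the share of continuers nor the time course of any effect is given.

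The figures assume that the protocol's 2.5-year and 96-week statements describe continuers and that the treatment runs without a gap. The second assumption does not hold for all: Study 111 subjects (33 of 1,044, 3.2%) had to complete the parent Safety Follow-up Visit first.

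On exposure, the natural reading of SAP 9.5 is time within Study 110, so the 26% is a risk to be closed by wording, not a demonstrated error. The change is worth making before the tables are programmed. It does not affect any hypothesis test.

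**What to change.** 1. **By-visit outputs.** Present by-visit safety changes, laboratory shifts and liver-test plots by treatment received immediately before Study 110 (TEZ/IVA, ivacaftor, placebo; Study 108 by Period 2 treatment), beside the pooled column. Footnote that Study 108 subjects on placebo in Period 2 had active drug in Period 1, and that some subjects, such as those from Study 111, had an off-drug gap. Define these groups for the Safety Set. SAP 9.7.3 needs that definition anyway, since it reports ECG threshold events by treatment group.
2. **Exposure.** Reword SAP 9.5 so that the denominator of exposure-adjusted Study 110 rates is time within the 110 TE Period, and report exposure since first active dose separately.
3. **Optional supplement.** Add one table of treatment-emergent events by system organ class and preferred term over the first-active-dose TE Period already defined in SAP 9.1. Leave out discontinuation and death rows, identify ivacaftor-alone time, and note that parent-study time comes only from subjects who completed and rolled over.

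The cost is more output, smaller groups, and the work of extending the SAP 7.1 group definitions to the other parent studies, whose designs are not fully described in these documents. No new data are collected and no parent-study by-visit safety data need re-windowing.
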